4.6 Discontinuation of Study Treatment, Withdrawal, and Compliance

Treatment duration is 2 years. Patients may continue drug beyond two years if, in the opinion of the treating physician, the patient is benefitting from treatment and benefits outweigh any risks of therapy

Discontinuation from the study treatment does not mean discontinuation from the study. The subject will be considered in follow-up, study procedures should still be completed as indicated by the study protocol, and AEs/SAEs will continue to be reported according to this protocol.

In the absence of treatment delays due to adverse events, study treatment/intervention may continue until:

- Disease progression per PCWG3 guidelines
- General or specific changes in the subject's condition renders the subject unacceptable for further treatment in the investigator's judgment.
- An inter-current illness that prevents further treatment administration.
- The subject decides to withdraw from the study.
- The subject has significant noncompliance with the protocol (see below).
- Unacceptable adverse event(s) and/or dose level reduction beyond requirements as detailed in this protocol.
- The clinical need for concomitant therapy that is not permitted in the study.
- Subjects who sign the informed consent form, enroll and receive the study intervention, but subsequently withdraw, or are withdrawn or discontinued from the study will not be replaced.

Progression of disease

Progression of disease per PCWG3 is defined as one or more of the following:

PSA progression

Recognize that a favorable effect on PSA may be delayed for \geq 12 weeks, even for a cytotoxic drug. Monitor PSA by cycle but plan to continue through early rises for a minimum of 12 weeks unless other evidence of progression.

If there is a decline in PSA from baseline: record time from baseline to the first PSA increase that is $\geq 25\%$ and ≥ 2 ng/mL above the nadir, and which is confirmed by a second value ≥ 3 weeks later (i.e., a confirmed rising trend).

If there is no decline in PSA from baseline but stable PSA at 12 weeks: PSA progression will be defined as $\geq 25\%$ and ≥ 2 ng/mL from PSA at 12 weeks .

Radiographic progression

Radiographic progression will be assessed per RECIST 1.1. Any new unequivocal bone lesion is considered progression, except if that lesion appears in the first post-treatment scan; in that

case, document the event, continue treatment until two additional new lesions appear, and record both events.

Consent Withdrawal

A subject may decide to withdraw from the study at any time. MCWCC CTO will follow their IRB of record's SOPs regarding consent withdrawal.

If a subject intends on withdrawing consent, staff should confirm which of the following options the subject chooses and document the discussion:

- Full consent withdrawal, with no study follow-up.
- Selective consent withdrawal from the interventional portion of the study but agree to continued follow-up of associated clinical outcome information.

Investigator-initiated Withdrawal

The investigator will withdraw a subject whenever continued participation is no longer in the subject's best interests. Reasons for withdrawing a subject include, but are not limited to, disease progression, the occurrence of an adverse event or a concurrent illness, a subject's request to end participation, a subject's noncompliance, or simply significant uncertainty on the part of the investigator that continued participation is prudent. The reason for study withdrawal and the date the subject was removed from the study must be documented.

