Pacritinib Dosage Modifications	Pacritinib dosage may be interrupted or modified for pacritinib-related hematologic toxicities, hemorrhage, severe infections, cardiac toxicities (including QTcF interval prolongation and reduction in ejection fraction), diarrhea, and other pacritinib-related nonhematologic toxicities. Pacritinib dosage may also be held for invasive procedures or at the discretion of the investigator. Refer to Section 5.2 for pacritinib dosage management guidelines.
Safety	Safety and tolerability will be assessed primarily by the incidence, severity, and change from baseline in safety parameters, such as treatment-emergent AEs (TEAEs; including SAEs), laboratory values, cardiac assessments, and vital signs.

STUDY SCHEMA

RT-radiation therapy
BID- twice a day
ADT-androgen deprivation therapy
LN-lymph node
DT-doubling time

STUDY CALENDAR

Study Assessments	Screening ¹		Cycle 1 ²		Cycle 2		Cycle 3		Cycle 4		Cycle 5		Cycle 6 and beyond (Treatment till progression)		End of treatment ¹ (EOT) visit ± 7 ⁴	Follow-up (2 years) ³
	Day - 30 to -1	Day - 30	Each Cycle (28 days)												30-day post-last dose Safety Visit (±7 days)	Every 6 months post EOT visit (±21 days)
Informed consent	X				1	15±3	±3	±3	±3	±3	±3	±3	Every 2 months (± 7 days)	Progression + - 7 ⁴		
Medical History ¹¹	X															
AE reporting			Recorded from Day 1 through 30 days after the last dose of study drug.													
Concomitant Medications			Recorded from the signing of the ICF through 30 days after the last dose of study drug.													
Physical Exam	X	X			X	X	X	X	X	X	X	X	X	X	X	X
Vital Signs ⁴	X	X			X	X	X	X	X	X	X	X	X	X	X	X
ECOG Performance Status	X	X			X	X	X	X	X	X	X	X	X	X	X	X
12-lead ECG ⁵	X	X				X				X		X	X ⁶			
Transthoracic echocardiogram (TTE) ⁶	X					X				X		X	X ⁶			
Comprehensive Geriatric Assessment	X										X					
Tissue for STAT 5 analysis ¹⁰	X															
Serum PSA	X	X				X	X	X	X	X	X	X	X	X	X	X
Serum Testosterone	X															
CBC w/ Diff	X	X			X	X	X	X	X	X	X	X	X	X	X	X
Blood Chemistry ⁸	X	X			X	X	X	X	X	X	X	X	X	X	X	X

Study Assessments	Screening		Cycle 1 ²	Cycle 2	Cycle 3	Cycle 4	Cycle 5	Cycle 6 and beyond (Treatment till progression)	End of treatment ¹ ² (EOT) visit	Follow-up (2 years) ³
	Each Cycle (28 days)		(in Days)		Every 2 months (± 7 days)		Every 2 months (± 7 days)	30-day post-last dose Safety Visit (±7 days)	Every 6 months post EOT visit (±21days)	
	Day -30 to -1	1	15±3	±3	±3	±3	±3	Progression +/ -		

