Coagulation (PT/PTT) and Hb A1C	X									
Research blood draw	X		X		X				X	
CT of Abdomen and Pelvis. /CT urogram/MRI abdomen and pelvis/PET ^{9, 13,15}	X				X				X	
Bone scan ^{9, 13,15}	X				X				X	
Chest Imaging ^{9,15}	X								X	
Pacritinib dispense	X ⁷		X ⁷	X	X	X ⁷	X ⁷		X	
Patient-reported outcome instrument: - FACT-P	X					X				

1. All screening procedures must occur within 30 days prior to treatment initiation.
2. Day 1 assessments are required to be performed prior to initiation of study treatment and can be performed up to 24 hours prior to initiation of study treatment. Study days are to be counted based on the start of treatment.
3. If a subject has disease progression or subject withdrawal, then they will be followed as per follow-up requirements. Patients will be in follow up for 2 years from EOT visit.
4. Vital signs include systolic and diastolic blood pressure, pulse, respiratory rate, temperature, and body weight.
5. A 12-lead ECG (collected in triplicate), including QTcF, will be performed at Screening, and then predose at C1D1, C2D1,, C5D1, C7D1, and every four months (every other cycle/odd cycles) thereafter provided normal QTcF.. if QTc is prolonged, more frequent monitoring will be done after discussion with sponsor. For patients who have discontinued treatment, ECGs are to be performed at the End-of-Treatment Visit but are not otherwise required
6. TTE will be performed at screening, C2D1, C5D1, C8D1, and every six months thereafter (every 3 cycles) provided normal LVEF and no

clinical evidence of heart failure. Window for all TTEs is -14 days from Day 1 of the cycle it is due for.

7. On days when ECGs are to be obtained, Pacritinib will be administered in the clinic to facilitate the performance of pre-dose assessments
8. Serum chemistry values will include AL T/SGPT, AST/SGOT, alkaline phosphatase, bilirubin (total, direct, and indirect) creatinine, LDH, sodium, potassium, chloride, bicarbonate, calcium, phosphate, magnesium, BUN/urea, albumin, glucose, cholesterol (fasting not required), and uric acid. Serum chemistry results obtained from unscheduled visits should be entered into the electronic database.
9. Additional serum chemistry testing should be done as clinically indicated.

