10. Unscheduled visits should include physical examination, laboratory tests, and radiographic evaluations as clinically indicated in the judgment of the investigator and these results must be entered into the clinical database (e.g., electronic data capture). Additional visits may be required for patients who have pacritinib dose modifications due to hematologic, cardiac, diarrhea, or other non-hematologic toxicities. Results of clinical laboratory assessments at unscheduled visits should be entered into the electronic database.
11. Core biopsy or surgical specimens from primary prostate cancer prior to administration of Jak2 inhibitor as well as other archive tissue (if available) will be used for study biomarker assessments. Tissue from surgical specimen will be preferred over core biopsy specimens when available. One hematoxylin and eosin slide and five unstained slides from formalin-fixed, paraffin-embedded pathology blocks with cancer will be reserved for study labs/biomarkers. If adequate tissue is not available, the patient would still qualify and be enrolled to the study.
12. Treatment duration is expected to be 2 years. Patients may continue drug beyond 2 years, if in the opinion of the treating physician, the patient is benefitting from treatment and benefits outweigh the risks of therapy.
13. imaging due at Cycle 4 has a 14-day window
14. If any of the required progression assessments have already been completed in the last 30 days, at the treating physician's discretion, they do not need to be repeated.
15. If PSMA/Axumin PET imaging is performed at baseline, other imaging is not required in addition to PET. Different modalities may be used at each imaging timepoint based on treating provider and insurance preference.

LIST OF ABBREVIATIONS

AE	Adverse Event
ALP	Alkaline Phosphatase
ALT	Alanine Aminotransferase
ANC	Absolute Neutrophil Count
AST	Aspartate Aminotransferase
AUC	Area Under the Curve
BUN	Blood Urea Nitrogen
CBC	Complete Blood Cell (Count)
CDK	Cyclin-Dependent Kinases
CQ	Chloroquine
CR	Complete Response
CRC	Clinical Research Coordinator
CRF	Case Report Form
CSF	Cerebral Spinal Fluid
CT	Computerized Tomography
CTCAE	Common Terminology Criteria for Adverse Events
CTL	Cytotoxic T Cell
CTO	Clinical Trials Office
DFS	Disease-Free Survival
DLT	Dose-Limiting Toxicity
DSMC	Data and Safety Monitoring Committee
DSMP	Data and Safety Monitoring Plan
ER	Estrogen Receptor
FDA	Food and Drug Administration
GCP	Good Clinical Practice

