4.1 Subject Status

Subject statuses throughout the trial are defined as follows:

- Prescreening: preconsent (subject considering trial or study staff considering a patient for the trial per institutional recruitment methods).
- Screening: the period after the consent, but prior to eligibility confirmation.
- Consented: consented, prior to eligibility confirmation.
- Eligible: the local investigator confirms all eligibility criteria apply.
- On study/enrolled: date eligibility is confirmed.
- On arm: date of enrollment.
- On treatment: first-day treatment was given to the last day treatment was given.
- Off treatment: the last day treatment was given.
- On follow-up: from the last day of treatment to the end of the follow-up period.
- Off study: follow-up period completed, with no additional data gathered.
- Withdrawn: subject fully withdraws consent (i.e., refuses ALL follow-up, even survival) or is taken off the study by the local principal investigator.

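### Men who stop pacritinib before about month 5, and possibly men still on drug, have no clearly scheduled PSA close to the six-month landmark

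*Combined protocol and SAP*

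**What the plan says.** Section 2.4 makes six-month PSA-progression-free survival the primary endpoint.

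Section 4.1 defines follow-up status by the end of dosing: "On follow-up: from the last day of treatment to the end of the follow-up period". Section 4.6 says that stopping treatment is not leaving the study, and continues: "The subject will be considered in follow-up, study procedures should still be completed as indicated by the study protocol". It gives no PSA interval for a man off drug.

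The Study Calendar has three relevant column headings:
- from Cycle 6, on treatment: "Every 2 months (± 7 days"
- end of treatment (EOT): "30-day post-last dose Safety Visit (±7 days"
- follow-up: "Every 6 months post EOT visit (±21 days"

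Serum PSA is listed at these visits. Calendar footnote 3 describes the route to follow-up more narrowly: "If a subject has disease progression or subject withdrawal, then they will be followed as per follow-up requirements". A stop for toxicity is not named there. The footnote on unscheduled visits adds: "Results of clinical laboratory assessments at unscheduled visits should be entered into the electronic database". Such visits take place as clinically indicated.

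For a man whose PSA has declined, 4.6 says to "record time from baseline to the first PSA increase" that meets the threshold, confirmed by a second value at least three weeks later. Section 8.4 uses a Kaplan-Meier estimate with a z-test. Section 8.10 censors a man with a missing primary outcome when he was last known to be alive and progression-free.

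**The concern.** A landmark endpoint needs an assessment close to the landmark. If PSA is next drawn well after month 6, a progression that occurred before month 6 is found late. Dated at the visit where it is found, it falls after the landmark, and the man counts as progression-free at six months. In a single-arm trial against a fixed 50%, that error favours the drug and no control arm offsets it.

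Early stops without progression can be expected. Section 3.1 treats a toxicity hold of more than 28 days as discontinuation, and sections 5.2.1 to 5.2.3 list toxicities that end treatment. At the interim analysis on 10 men, one such man is a tenth of the core data.

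**Working it through.** The plan states no figure on this point, so there is none to reproduce. The check is visit arithmetic, followed by an illustrative size.

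**Inputs from the documents.** 28-day cycles; EOT at last dose + 30 days (±7); follow-up at EOT + 6 months (±21 days); two-monthly visits from Cycle 6; null value 50%; 46 men. I take month 6 as day 183 and two months as 61 days.

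**Assumptions.** Exponential time to progression with median 183 days; 5%, 10% or 20% of men stop early, with last dose L uniform on days 15 to 120; hazard unchanged after stopping; progression dated at the next PSA.

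**1. Which stops have no PSA between EOT and month 6 (follow-up column applied).**
- Earliest possible follow-up PSA, for a stop on day 1: 1 + 30 − 7 + 183 − 21 = day 186, after day 183.
- Latest possible EOT for a stop on day 145: 145 + 30 + 7 = day 182, before day 183.
- Ignoring windows, EOT precedes day 183 when L < 153, which is about month 5.

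**2. Length of the unobserved stretch before day 183 for early stoppers.** Gap = 183 − (L + 30).

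| Last dose (day) | EOT PSA | Next PSA | Gap before day 183 |
|---|---|---|---|
| 29 | 59 | 242 | 124 days |
| 57 | 87 | 270 | 96 days |
| 85 | 115 | 298 | 68 days |
| 113 | 143 | 326 | 40 days |

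**3. The same gap for men still on drug.** Cycle 6 Day 1 is 1 + 5 × 28 = day 141. The calendar allows two readings.
- Reading A: a visit on day 141, the next on 141 + 61 = day 202. Gap 183 − 141 = 42 days.
- Reading B: the first two-monthly visit is 61 days after Cycle 5 Day 1 (day 113), on day 174. Gap 183 − 174 = 9 days.

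Stopping leaves a longer gap than staying on drug when 183 − (L + 30) exceeds 42 (L < 111) or 9 (L < 144).

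**4. Size for men on drug under late dating.** The month-6 estimate becomes S at the last PSA before day 183, with S(t) = 2^(−t/183).
- Reading A: S(141) = 58.6% against a true 50%, so +8.6 points.
- Reading B: S(174) = 51.7%, so +1.7 points.

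These take all men as on drug to month 6.

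**5. Extra size from early stoppers under late dating.** A stopper's estimate becomes S(L + 30). Its mean over L = 15 to 120 is [S(45) − S(150)] / (λ × 105), with λ = ln 2 / 183 = 0.003788:

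(0.8433 − 0.5666) / 0.3977 = 0.696.

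The increment over the on-drug schedule is f × (0.696 − 0.586) for A and f × (0.696 − 0.517) for B.

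| Stop fraction f | A, formula | A, simulated | B, formula | B, simulated |
|---|---|---|---|---|
| 5% | 0.55 | 0.55 | 0.89 | 0.91 |
| 10% | 1.10 | 1.11 | 1.78 | 1.82 |
| 20% | 2.19 | 2.20 | 3.57 | 3.60 |

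Simulated values are from 20,000 trials of 46 men, in percentage points. The result depends on when men stop. At f = 20%, stops on days 15 to 60 give 3.80 (A) or 5.20 (B); stops on days 60 to 145 give 0.44 or 1.83.

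**6. Early stoppers censored at EOT instead (8.10).** With unchanged hazard the simulated shift is −0.15 to −0.69 points. If the hazard doubles after stopping it is +0.25 to +1.55.

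**7. Scale.** The binomial standard error at 50% with 46 men is √(0.25/46) = 7.4 points.

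**The case against.** **The gap depends on the reading.** Footnote 3 sends men to follow-up only on progression or withdrawal, and 4.6 asks for PSA to be monitored each cycle. One could conclude that a man who stops for toxicity stays on the cycle schedule. This stands as a possible reading. But the cycle sentence concerns staying on treatment through early rises, 4.1 starts follow-up at the last dose, and no sentence keeps cycle PSA after a toxicity stop. The calendar's marks also cannot be aligned to every visit with certainty in the text available, although the EOT and follow-up headings are legible. Unscheduled PSA would shrink the gap, but nothing requires it.

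**The plan already has a censoring rule.** Sections 8.4 and 8.10 set Kaplan-Meier with censoring, which is close to neutral for early stoppers if the hazard is unchanged. This largely stands. It does not help when a later visit reveals the progression and the event is dated there.

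**Early stopping may be uncommon.** Section 5.2.1 is strict on grade 3 or higher toxicity, but Tables 1, 4 and 5 allow many toxicities, including some of grade 3, to be held and treatment resumed. It would be wrong to infer that most such toxicity ends treatment. The only discontinuation figure for adverse events, 17.4%, comes from the myelofibrosis dose-finding study in section 1.5.4, a different population.

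**Late confirmation.** A reader might infer that a rise first seen at EOT is lost because the next scheduled PSA is 183 ± 21 = 162 to 204 days later. The documents do not support that. The three-week rule has no upper limit, the event is dated at the first rise, and the no-decline rule states no confirmation. Late confirmation can matter only at a data cut-off such as the interim.

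**Unknowns as failures.** A reader might also infer a large loss of power because men without a month-6 PSA count as failures in the 27-of-46 rule of 8.3. No section says so.

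**Conclusion.** The concern holds as a scheduling weakness. On the natural reading, a stop without progression before about month 5 leaves no scheduled PSA between EOT and month 6. The schedule for men on drug may leave the same kind of gap, and if the next visit is day 202 that gap matters more: up to about 8.6 points at a true 50%, against 0.6 to 3.6 further points from early stoppers at assumed rates of 5% to 20%.

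Both figures assume dating at the next visit, and both favour the drug. If the first two-monthly visit is day 174, the on-drug figure falls to about 1.7 points. The documents give no early-stop rate for this population and no hazard after stopping, so the early-stopper sizes are illustrative and small beside a standard error of 7.4 points. Unlike sampling error, though, this error has a known direction under late dating and can be removed before data are seen.

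The documents do not establish that the schedule biases the result whatever the handling: censoring early stoppers at the last PSA is roughly neutral unless the hazard changes after stopping. This is a cheap improvement, not a fatal flaw.

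**What to change.** State in the Study Calendar and in 4.6 that, whatever the treatment status, PSA continues on the on-treatment schedule until PSA progression, new antineoplastic therapy or withdrawal of consent. Add a PSA at month 6 (about day 183, with a narrow window) for every man still free of those events, on or off drug. Align footnote 3 with this, so that a toxicity stop does not move a man to six-monthly PSA before the landmark.

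The cost is a protocol wording change and a few extra routine PSA draws.

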Department of Urology
[name]
[name]
[contact]
Email: [contact]

Sub-Investigator:

[name]
Professor
Department of Pathology
[name]
[name]
[contact]
Email: [contact]

Sub-Investigator:

[name]
Associate Professor
Department of Radiology
[name]
[name]
[contact]
Email: [contact]

Sub-Investigator:

[name]
Associate Professor
Department of Radiation Oncology
[name]
[name]
[contact]
Email: [contact]

Sub-Investigator:

[name]
Professor
Department of Urologic Surgery
[name]
[name]
[contact]
Email: [contact]

Sub-Investigator:

[name]
Professor
Department of Radiation Oncology
[name]
[name]
[contact]
Email: [contact]

Sub-Investigator:

[name]
Assistant Professor
Department of Radiation Oncology
[name]
[name]
[contact]
Email: [contact]

Biostatistician:

[name]
Associate Professor
Institute for Health and Society
Division of Biostatistics
[name]
[name]

[contact]
Email: [contact]

Funder:
MCW Cancer Center

Drug supply
CTI BioPharma

[figure not shown]
PROTOCOL SUMMARY

Title	A Phase 2 Study of Pacritinib for the Biochemical Relapse after Definitive Treatment for Prostate Cancer
IND Sponsor	Investigator-Sponsor
Principal Investigator	[name]
Clinical Trial Phase	Phase 2
Study Population	Patients with histologically or cytologically confirmed prostate adenocarcinoma, status post definitive treatment and biochemical recurrence.
Primary Objectives	To determine the effect of pacritinib on the time to PSA progression in patients with biochemical relapse of prostate cancer (defined as the length of time that a given subject will be alive and free from PSA progression per PCWG3 guidelines).
Secondary Objectives	
 1. To evaluate the absolute PSA nadir as a result of treatment. 2. To determine the time to PSA nadir from the start of treatment. 3. To determine the time to subsequent antineoplastic therapy 4. To determine the effect of investigational treatment on testosterone levels 5. To determine the safety and toxicities of the study drug.

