4.5 Eligibility Confirmation

Study staff must adhere to MCWCC CTO SOPs regarding eligibility review/confirmation.

No waivers of protocol eligibility will be granted. When clinical factors relating to an eligibility item are unclear or questionable, the MCW PI can only provide guidance or clarification on eligibility. Any eligibility questions should be directed to [name] at [contact].

Inclusion Criteria

1. Patients aged \geq 18 years.
2. Histologically or cytologically confirmed prostate adenocarcinoma.
3. Prior radical prostatectomy or definitive radiation.
4. Biochemically recurrent prostate cancer with PSA doubling time \leq 9 months at the time of study entry (calculated per MSKCC prostate nomogram: https://www.mskcc.org/nomograms/prostate/psa_doubling_time). Calculation of PSA doubling time should include the use of all available PSA values obtained within the past 12 months prior to randomization, with a minimum of three values separated by at least two weeks apart. The PSA values used to calculate the PSA doubling time must all be \geq 0.1 ng/mL and should be measured in the same laboratory whenever feasible.
5. Prior adjuvant or salvage radiation or not a candidate for radiation based upon clinical assessment of disease characteristics and patient comorbidities. (N/A for patients who underwent definitive radiation therapy).
6. Screening PSA $>$ 0.5 ng/mL.
7. No definitive evidence of metastases on screening imaging per the judgment of the investigator. Pelvic lymph nodes measuring 1.5 cm or less in short axis diameter are allowed. Lesions identified on imaging modalities (e.g. PSMA or choline PET) that are not visualized on CT and/or MRI or radionuclide bone scan are allowed. Equivocal lesions on bone scan should be followed up with additional imaging as clinically indicated.
8. Screening serum testosterone $>$ 50 ng/dL.
9. Eastern Cooperative Oncology Group (ECOG), Performance Status grade 0-1 or Karnofsky Performance Status \geq 70.
10. No prior JAK2 inhibitor treatment.
11. Male patients, even if surgically sterilized (i.e., status post-vasectomy), must agree to one of the following:
 - Practice effective barrier contraception and another effective method of birth control if he is having sex with a woman of childbearing potential during the entire study period and through 90 calendar days after the last dose of study agent
12. Ability to understand a written informed consent document, and the willingness to sign it.

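### The PSA-progression rule behind the primary endpoint gives *stable at week 12* no number and writes no event for a PSA that never fell and is already rising then; Section 8 supplies no operational PSA rule

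*Combined protocol and SAP*

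**What the plan says.** The primary endpoint (Section 2.4) is six-month PSA-progression-free survival. The Protocol Summary describes it as time "alive and free from PSA progression per PCWG3 guidelines". PCWG3 is cited there and in Section 4.6, but not reproduced.

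Section 4.6 writes out two PSA branches:

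- **Decline from baseline.** The instruction is to "record time from baseline to the first PSA increase that is" at least 25% and at least 2 ng/mL above the nadir, confirmed by a second value at least 3 weeks later.
- **No decline.** "If there is no decline in PSA from baseline but stable PSA at 12 weeks: PSA progression will be defined as" at least 25% and at least 2 ng/mL, measured from the week-12 value. No confirmation is stated.

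On early rises the section says: "Monitor PSA by cycle but plan to continue through early rises for a minimum of 12 weeks unless other evidence of progression". That concerns continuing treatment. It gives no event status.

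Sections 8.3, 8.4 and 8.9 count patients alive without PSA progression at six months. They test the rate against 50% (success at 27 or more of 46) and use the same event for futility after 10 patients. Section 8.10 adds a censoring rule. None of them gives a PSA threshold, reference value, confirmation or event date, or points to Section 4.6.

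Inclusion criterion 4 (Section 4.5, Eligibility Confirmation) requires "Biochemically recurrent prostate cancer with PSA doubling time" of 9 months or less, calculated "with a minimum of three values separated by at least two weeks apart".

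**The concern.** The two written branches do not cover every patient. A man whose PSA never falls and is climbing at week 12 belongs to neither branch unless *stable* is read loosely enough to include him. The entry criterion selects men with rapidly rising PSA, so this is the ordinary course if the drug does nothing.

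Two readings of *stable* are natural: a rise under 25%, or the joint threshold (25% and 2 ng/mL) not yet met. They classify most untreated patients differently. On either reading, a stable patient is then measured from week 12, which discards the first 12 weeks of growth.

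The trial has one arm and a fixed 50% comparator, so no control group absorbs a shift in scoring. It is also open-label, so a rule left unwritten could be settled after the PSA curves are known.

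**Working it through.** **The plan's own figures.** A median of 10 months with exponential times gives a six-month rate of exp(-ln 2 × 6/10) = 66.0%, as stated. The designed effect is 66 - 50 = 16 points. The exact chance of passing stage 1 (5 or more of 10) and reaching 27 of 46 is 13.3% at a true rate of 50%. The plan states 10%; that difference is a separate matter. For scale, the chance becomes 32.4% at a true rate of 55% and 57.7% at 60%.

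**Inputs from the documents.** Entry PSA above 0.5 ng/mL; doubling time (DT) at most 9 months; thresholds of 25% and 2 ng/mL; week 12 = day 84 = 84/30.4375 = 2.76 months.

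**Assumptions.** The documents give no PSA or DT distribution. Assumed: PSA(t) = P0 × 2^(t/DT), no drug effect, no deaths, no assay noise; DT uniform on 2-9 or 3-9 months; log-normal baseline PSA truncated at 0.5, with median parameter 1, 1.5, 2.1 or 3 and log-SD 0.6, 0.8, 1.0 or 1.2. That makes 2 × 4 × 4 = 32 scenarios.

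**Step 1: growth by week 12.** The rise is 2^(2.76/DT) - 1: 24% at DT 9 months, 38% at 6 and 89% at 3. It stays under 25% only if DT exceeds 8.57 months, which is (9 - 8.57)/7 = 6% or (9 - 8.57)/6 = 7% of patients. On the joint reading, 60-99% are stable at week 12.

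**Step 2: two patients.**

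- P0 4.0, DT 9 months: 4.95 at week 12 (+24%, stable on both readings) and 6.35 at month 6. That is +2.35 over baseline but +1.40 over week 12, so no event under the written branch.
- P0 1.5, DT 4 months: 2.42 at week 12 (+61%, stable only on the joint reading) and 4.24 at month 6. That is +2.74 over baseline but +1.82 over week 12. On the joint reading there is no event; on the 25% reading no branch applies.

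**Step 3: baseline PSA needed for an untreated event by month 6.** From baseline: 2/(2^(6/DT) - 1). From week 12: 2/(2^(6/DT) - 2^(2.76/DT)). The 25% condition is met in each row.

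| DT (months) | Baseline reference | Week-12 reference |
|---|---|---|
| 9 | 3.4 ng/mL | 5.7 ng/mL |
| 6 | 2.0 | 3.2 |
| 4 | 1.09 | 1.65 |

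Patients between the two values change status with the reference.

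**Step 4: six-month event-free rate on an inert drug, range over 32 scenarios.**

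| Rule | Rate |
|---|---|
| Stable = rise under 25%; others progressed | 4-7% |
| Stable = rise under 25%; others no event | 98-100% |
| Stable = joint threshold not met; others progressed | 40-90% |
| Stable = joint threshold not met; others no event | 73-91% |
| Week-12 reference for all | 40-90% |
| Baseline reference for all | 22-76% |

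Within a scenario, the week-12 reference exceeds the baseline reference by 13-23 points. The two fall on opposite sides of 50% in 12 of 32 scenarios.

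**Step 5: timing of the last PSA (secondary).** The calendar table is damaged. Its later columns read "Every 2 months (± 7 days", while an ECG footnote lists "C5D1, C7D1, and every four months (every other cycle/odd cycles) thereafter". If the last PSA before six months is at day 168, the gap is 13-28 points; at day 140 it is 9-39.

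**The case against.** - **The week-12 reference is deliberate.** Section 4.6 says that a favourable PSA effect may take 12 weeks or more to appear. This stands: the choice has a stated reason, and a baseline reference is a preference, not a correction of an error. It does not supply a number for *stable* or the missing case.
- **PCWG3 may fill the gap.** It may. A reader might infer that the rising case has no rule anywhere, and the documents do not support that. But Section 4.6 presents its own branches as the definition, and those are incomplete.
- **Section 8 is not silent.** A reader might infer that it has no event rule at all. It names death or PSA progression and a censoring rule; only the operational PSA rule and a pointer to Section 4.6 are missing.
- **The spread can be overstated.** Setting the baseline reference, the week-12 reference and the two joint readings side by side gives a within-scenario spread of 15-54 points at six months. Baseline is not a reading of the no-decline branch; without it the spread is about 1-40 points. If patients not stable on the joint reading count as progressed, the six-month rate equals that of the week-12 reference for all. The large ambiguity lies between the joint and the 25%-alone readings.
- **The model has no assay noise.** This stands. A chance dip below baseline would move a patient to the nadir branch, which has no week-12 reference.

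**Conclusion.** The concern holds as an incomplete definition of the only efficacy event that the trial tests, and it should be fixed before outcomes are read. The gap in the text needs no model: *stable* is unquantified, the never-declined and rising case is unwritten, confirmation is stated for one branch only, and Section 8 does not close these gaps.

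The size rests on the growth model and the assumed PSA mix. With patients who are not stable counted as progressed, an inert drug scores 4-7% or 40-90% event-free at six months, depending on what *stable* means. The week-12 reference adds 13-23 points over baseline, comparable with the whole designed effect of 16 points.

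A reader might go further and infer that the wording alone decides whether an inactive drug passes 50%. The documents do not support that. Baseline and week-12 references fall on the same side of 50% in 20 of 32 scenarios at six months, and the PSA mix, which the plan does not give, matters at least as much. The day-140 figures should carry little weight, because they depend on a damaged calendar.

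**What to change.** For endpoint scoring only, and before outcomes are read, add one paragraph to Section 8 with a PSA event rule that covers every patient:

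1. Give *stable at week 12* a number, and state the event and its date for a patient with no decline who is rising at week 12. If PCWG3 is taken to supply this case, write the text out.
2. Preferably, measure no-decline patients from baseline: at least 25% and at least 2 ng/mL above baseline, at or after week 12. Keep the nadir rule for patients who declined.
3. Apply confirmation at least 3 weeks later to both branches, and require the confirming value to be no lower than the first qualifying value. An early peak that is already falling is then not scored as progression, which respects the delayed-effect rationale.
4. Date the event at the first qualifying value, and name the last scheduled PSA that counts for six months.
5. Report the other reference (week 12 or baseline) as a sensitivity analysis, whichever is primary.

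The cost is one paragraph and one extra analysis of PSA values already collected. With a baseline reference the observed rate may be lower (13-23 points for an inert drug under the assumptions above), so a positive result is harder to reach. Power for an active drug under the revised rule has not been worked out here. The 2 ng/mL floor stays, so slow risers with low PSA still cannot have an event by six months.

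Sections 4.6 and 5.1.2 also use progression to govern stopping of treatment. The sponsor should reconcile that use with the endpoint definition; no stopping rule is proposed.
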